### Sample Size

The total sample size of 50 patients accounts for the likely scenario in which up to 15% of patients will not have full datasets due to loss-to-follow-up or unusable MRI data (e.g. patient motion, abnormal brain MRIs). Based upon the results of the phase 2 and 3 trials of erenumab and the fact that this is an open-label study, we anticipate that approximately 50% of patients will be “responders” at 8 weeks. (6-8) Thus, we would have at least 21 responders and 21 non-responders for this analysis, a sample size that is adequate for the imaging and multivariate modeling aims of this study. Sample size was determined by calculating the number of subjects needed per group to detect a difference in pain induced BOLD signal of 0.1% pre-erenumab to post-erenumab, assuming a standard deviation of 0.1. Based on a type I error of .05, a sample size of 21 patients per group will give 88% power to detect pre-treatment to post-treatment differences for responders and non-responders. The use of % signal change as the measure for calculating effect size is the standard recommendation when determining sample size for fMRI studies.(41)

Desmond and Glover, in their paper entitled “Estimating sample size in functional MRI (fMRI) neuroimaging studies: statistical power analyses”, used data from fMRI studies of cognitive function and somatosensory stimulation to estimate sample sizes needed for fMRI studies. [Desmond 2002] They concluded that for a threshold of 0.05, about 12 subjects are required to achieve 80% power at the single voxel level for typical activations. However, they state that at more realistic thresholds that approach those used after correcting for multiple comparisons, the number of subjects doubles (n=24) to maintain this level of power.

As Mumford and colleagues point out, the number of stimulations/events that are included in the fMRI paradigm must also be considered when calculating power – the more stimulations/events, the greater the power to detect a difference.(41)

Russo et. al. used a similar study design as the one we have proposed to investigate pain-induced activations in migraine pre- and post-external trigeminal neurostimulation. [Russo 2017] In the Russo study there was a pre- to post-treatment change in pain-induced activation of the anterior cingulate of approximately 0.2% with a standard deviation of approximately 0.1%. Given this effect size, a sample size of 16 individuals (81% of whom were responders) was adequate to demonstrate significant pre- to post-treatment changes in pain-induced activation of the anterior cingulate cortex.

With limited available data to ensure that our effect size will be as large as 0.2%, we are more comfortable powering the analysis for an effect size half of that found in Russo et. al. (i.e. 0.1%).(11) The resultant sample size is consistent with that recommended by Desmond and Glover and considers the impact of the number of painful stimulations as recommended by Mumford.(41, 42)

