#### Analysis Plans

*Specific Aim #1 (i.e. identify changes in brain structure and function that correlate with response to erenumab):* Pre-treatment and post-treatment MRI data will be used for within and between subject

comparisons. Within subject analyses will compare baseline brain activation and perfusion patterns and functional connectivity patterns pre-treatment to post-treatment. Between subject group analyses will compare post-treatment MRI data in erenumab responders to non-responders.

Similar comparisons will be made for pre- and post-treatment pain thresholds (i.e. results of quantitative sensory testing) and cognitive testing.

So as to help with the interpretation of differences between responders and non-responders, MRI data from erenumab-treated patients will be compared to healthy non-migraine control data that we have already collected during the conduction of previous studies, when available (although we have plenty of data for the majority of analyses, we have limited ASL data and no n-back data from healthy controls). Differences in brain structure and function of migraine patients prior to erenumab treatment compared to healthy controls will be identified. Results of this analysis will determine alterations of brain structure and functions in migraine patients compared to healthy controls. Areas where migraine patients show altered structure and function will be used as regions of interest (ROIs) to assess the longitudinal, within-group changes of erenumab responders and non-responders.

Although multiple analyses are planned using functional, structural, and perfusion data, the primary analysis for specific aim #1 will be the comparison of pre-treatment pain-induced regional activation strength vs. post-treatment pain-induced regional activation strength in erenumab responders and separately in erenumab non-responders.

Post-treatment changes in other measures of brain function as well as measures of brain perfusion, brain structure, cutaneous pain thresholds and cognitive function in those responding to erenumab and in those not responding will be explored.

Two-tailed T-Tests or Mann-Whitney U tests will be used to perform group comparisons on demographic and cognitive measures and on pain threshold data. Neuroimaging data will be analyzed using general linear model designs. Within-group changes on cognitive measures, sensory testing and neuroimaging data will be assessed by applying a general linear mixed model design.

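### The planned 21 patients per response group is an expectation, not a minimum, and the stated 88% is not shown to be the power of the within-group primary comparison

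*Combined protocol and SAP*

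**What the plan says.** The Sample Size section starts from 50 patients and allows that "up to 15% of patients will not have full datasets due to loss-to-follow-up or unusable MRI data". It anticipates a responder share of roughly one half at 8 weeks and concludes: "Thus, we would have at least 21 responders and 21 non-responders for this analysis".

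The power statement targets a 0.1% pre-to-post difference in pain-induced BOLD signal, "assuming a standard deviation of 0.1", with a type I error of .05, and reports that "a sample size of 21 patients per group will give 88% power to detect pre-treatment to post-treatment differences for responders and non-responders". It names no test, no sidedness and no within-patient correlation. It does not say whether the SD belongs to a single scan or to the change between scans.

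The same section describes the cited neurostimulation study as showing a "change in pain-induced activation of the anterior cingulate of approximately 0.2% with a standard deviation of approximately 0.1" percent. Because few data were available, the authors say that "we are more comfortable powering the analysis for an effect size half of that found in" that study.

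Under Analysis Plans, the primary analysis for Specific Aim 1 compares pre-treatment with "post-treatment pain-induced regional activation strength in erenumab responders and separately in erenumab non-responders". On method, the section says: "Within-group changes on cognitive measures, sensory testing and neuroimaging data will be assessed by applying a general linear mixed model design". Imaging Data Plans adds that cluster-threshold and multiple-comparison corrections will be applied.

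**The concern.** Two statements claim more than the section supports.

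First, an upper limit on losses can put a floor under the number of evaluable patients. An approximate response rate cannot put a floor under each response group. The Daily Headache Diary section defines responders by the change in migraine days in weeks 5–8, so the split is known only after treatment. Each group is tested separately, so the smaller group's size determines its own power.

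Second, the 88% is expressed per group, and the inputs as given reproduce it most directly with a test of two independent groups. The primary comparison uses two scans of the same patients. A reader cannot tell which calculation was done or what the 0.1 describes. If one group shows no significant change, that reader would rely on the 88% to interpret the result.

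**Working it through.** **Inputs.** From Sample Size: N = 50, loss up to 15%, response about 50%, difference 0.1, SD 0.1, type I error .05, 21 per group. Assumed here: two-sided tests; one pre and one post scan with complete data, for which the mixed model corresponds to a paired t test; pre/post correlation r of zero or more. Power is from the noncentral t distribution.

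**1. Group size.** 50 × 0.85 = 42.5 evaluable, and 42.5 × 0.5 = 21.25 per group. The plan's 21 is reproduced as an expected value.

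With the number of responders X ~ Binomial(N, 0.5), both groups reach 21 when 21 ≤ X ≤ N − 21:

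| Evaluable | P(both ≥ 21) | Mean size of smaller group |
|---|---|---|
| 42 | 12.2% | 18.4 |
| 43 | 23.9% | 18.9 |
| 50 | 79.7% | 22.2 |

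With 42, only an exact 21/21 split qualifies, and the smaller group has 17 or fewer in 28% of cases. If the true rate were 40% or 60%, the 12.2% would fall to 5.2%.

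**2. Reproducing the 88%.** Independent two-sample t test, 21 v 21: noncentrality = (0.1/0.1) × √(21/2) = 3.24 on 40 degrees of freedom. Power = 88.5%, which matches.

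**3. The within-group comparison, n = 21.**

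- If 0.1 is the SD of change: noncentrality = (0.1/0.1) × √21 = 4.58 on 20 degrees of freedom. Power = 99.2%. On this reading 12 patients would already give about 88%.
- If 0.1 is the per-scan SD: SD of change = 0.1 × √(2(1 − r)). At r = 0 this is 0.141 and the noncentrality is again 3.24, now on 20 degrees of freedom. Power = 86.9%. It is 90.1% at r = 0.1, 95.7% at r = 0.3 and 99.2% at r = 0.5. It equals 88% at r of about 0.03.

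At r = 0 the paired and two-sample tests share the same noncentrality and differ only in degrees of freedom. The figure alone therefore cannot show which test was used.

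**4. A smaller group, uncorrected 0.05.**

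| n | SD of change 0.1 | Per-scan SD 0.1, r = 0 |
|---|---|---|
| 21 | 99.2% | 86.9% |
| 18 | 97.9% | 80.7% |
| 16 | 96.2% | 75.3% |

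**5. Correction for multiple comparisons.** The plan gives no threshold or region count, so this is only an illustration. At a per-test alpha of 0.005 and n = 21, power is 90.6% (SD of change) or 54.6% (per-scan, r = 0). On the SD-of-change reading it stays at 88% or more down to an alpha of about 0.0036.

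**The case against.** A reader might infer that the authors used the wrong test, a two-sample calculation for a paired design. The documents do not establish that. A paired test with a per-scan SD of 0.1 and near-zero correlation also gives 87–88%. Such a low correlation between two scans of one patient may be unlikely, but the section neither states nor excludes it. What stands is that the basis of the figure is undisclosed.

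A reader might also infer that the study is underpowered. The figures do not support that. The section's description of the cited study favours reading 0.1 as the SD of change. On that reading power at 0.05 exceeds 88% even at 16 patients, and with 42 evaluable and 50% response the smaller group falls below 12 in only about 0.3% of cases. The target effect was also deliberately set at half the one cited.

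On multiplicity, the section discloses its .05 level and reports a published benchmark in which thresholds near corrected ones double the requirement from 12 to 24 subjects. Only a corrected power figure is missing, and it could not be computed firmly beforehand because the regions of interest come from the later patient–control comparison.

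On group size, 15% is the largest loss allowed for, so about 21 is the low end across losses of 0–15% if the split is exactly even. That explains the wording but ignores variation in the split. The Daily Headache Diary section does allow other response definitions and correlations with change in migraine frequency. These are not prespecified, so they mitigate only in part.

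**Conclusion.** The minimum of 21 per group is wrong as written. It is the expected split under the planned loss and an even response rate, and it is more likely than not to be missed in at least one group if the full 15% is lost.

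The 88% is not shown to be the power of the primary comparison. At 21 patients, uncorrected 0.05 and non-negative correlation, the paired power is 86.9% or higher, so 88% is about right or conservative. It is clearly too high only after a sufficiently strict multiplicity correction, or when a smaller group coincides with a per-scan SD and low correlation (80.7% at n = 18, r = 0). These results rest on treating the mixed model as a paired test and on the plan's own effect and SD. The defect is in the reporting of the design, not in its size, and is worth correcting.

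**What to change.** In Sample Size:

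1. Replace the minimum with: about 21 expected in each group if 15% are lost and 50% respond; groups may be unequal, with the smaller averaging about 18 and possibly lower.
2. Replace the 88% with the two-sided power of the within-group paired test. State whether 0.1 is the SD of change or the per-scan SD and, if per-scan, the assumed pre/post correlation. Give it for 21 patients and for a smaller group such as 18.
3. Label the figure as uncorrected for the multiple comparisons that Imaging Data Plans provides for.

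Two additions are optional: a short table of power over illustrative region counts, and a qualification of the statement that the sample size agrees with the published fMRI benchmark, since 21 lies between the cited 12 and 24.

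The cost is a few reworded sentences, with no change to enrolment or analysis. The single power figure becomes one that depends visibly on its assumptions and may be higher or lower than 88%.

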### Subject Recruitment and Screening

Subjects will be recruited from the Mayo Clinic Arizona Headache and Neurology clinics, from the clinical practices of colleagues practicing in the Phoenix region, and via posting of IRB-approved recruitment materials.

### Subject Compensation

Subjects will be compensated \$70 per research visit and \$30 per month during which they are at least 80% compliant with the headache diary (i.e. provide data on at least 80% of days in a 4 week period).

### Informed Consent

Informed consent procedures will be performed according to the requirements and recommendations of the Mayo Clinic Institutional Review Board. Written informed consent will be obtained from all subjects prior to their participation in this research. The informed consent process will be based upon principles discussed in the Declaration of Helsinki and in accordance with US 21CFR. Applicable HIPAA privacy notifications will be included. Participants will be given ample time and opportunities to ask questions about this study prior and following consent. All consent forms will require IRB approval prior to their use. Patients will always have the right and will be informed of their right to withdraw from the study at any time. De-identified data collected until the time of withdrawal will be included in further analyses. Enrolling clinicians will be made aware that the needs of their patients come first and thus the safety and wellbeing of study participants is of primary concern. The study will be done in accordance with the principles of Good Clinical Practice and with US Food and Drug Administration (FDA) and International Committee for Harmonization guidelines for safety monitoring. Any member of the research team who obtains informed consent from a subject will need to be approved by the Institutional Review Board. The informed consent process will occur in a location that is approved by the Institutional Review Board. Consent documents will be stored for a minimum of 3 years after conclusion of the study. The study participant will retain a copy of their signed consent document.

### Adverse Events

An adverse event is defined as any untoward medical occurrence in a clinical trial patient. The event does not necessarily have a causal relationship with study treatment. The investigator is responsible for ensuring that any adverse events observed by the investigator or reported by the subject are recorded in the patient's record. The definition of adverse events includes worsening of a pre-existing medical condition. Worsening indicates that the pre-existing medical condition or underlying disease has increased in severity, frequency, and/or duration more than would be expected, and/or has an association with a significantly worse outcome than expected. A pre-existing condition that has not worsened more than anticipated during the study or involves an intervention such as elective cosmetic surgery or a medical procedure while on study is not considered an adverse event.

### *Definition of Serious Adverse Events*

A serious adverse event is defined as an adverse event that meets at least 1 of the following serious criteria:

- fatal
- life threatening (places the subject at immediate risk of death)
- requires in-patient hospitalization or prolongation of existing hospitalization
- results in persistent or significant disability/incapacity
- congenital anomaly/birth defect
- other medically important serious event

An adverse event would meet the criterion of “requires hospitalization,” if the event necessitated an admission to a health care facility (e.g., overnight stay). If an investigator considers an event to be clinically important, but it does not meet any of the serious criteria, the event could be classified as a serious adverse event under the criterion of “other medically important serious event.” Examples of such events could include allergic bronchospasm, hypersensitivity reaction, or events that necessitate an urgent intervention.

*Reporting Procedures for Adverse Events That do not Meet Serious Criteria*

The investigator is responsible for ensuring that all adverse events observed by the investigator or reported by the subject that occur after the dose of investigational product through the end of the safety follow-up visit (8 weeks after the last dose of investigational product) are reported using the Adverse Event case report form. The Adverse Event case report form is included within the Appendix of this protocol.

The investigator must assign the following adverse event attributes:

- adverse event diagnosis or syndrome(s), if known (if not known, signs or symptoms)
- dates of onset and resolution (if resolved)
- intensity
- outcome
- action taken
- assessment of relatedness to investigational product

Assessment of whether the adverse event is possibly related to the investigational product is indicated by a “yes” or “no” response to the question: “Is there a reasonable possibility that the event may have been caused by the investigational product?”

The Adverse Event case report form will be completed by the member of the research team that receives the information from the participant about the adverse event. The Principal Investigator will always be responsible for initially and dating the form, indicating that the Principal Investigator has reviewed the adverse event with the research team member, determining the relationship of the adverse event to the study, and determining if the adverse event meets criteria for a serious adverse event.

*Reporting Procedures for Serious Adverse Events*

The investigator is responsible for ensuring that all serious adverse events observed by the investigator or reported by the subject that occur after signing of the informed consent through the end of the safety follow-up visit (8 weeks after the last dose of investigational product) are recorded in the subject’s record and to the local Institutional Review Board according to that Board’s policy.

Reporting of adverse events to Amgen will occur in accordance with the “Safety Data Exchange Requirements” as provided by Amgen. These requirements dictate the need for and timing of reporting adverse events to Amgen. A copy of the “Safety Data Exchange Requirements” has been included within the Appendix of this protocol.

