Additionally, noting that this study will collect both widely accessible imaging data such as that derived from T1-weighted sequences as well as less accessible types such as pain-induced functional activations, we aim to determine how widely useable our predictive model is in clinical practice. To achieve this goal, we will first limit our PSO-based feature selection to select only PCs derived from structural measures of T1-weighted sequences. Then we will compare the accuracy to that of another analysis allowed to select resting state functional connectivity data, followed by selection of additional PCs from more advanced imaging data. This result will help determine how much value is added when using advanced imaging data in predicting treatment response; and if advanced imaging is not available in a clinic, how good the predictive accuracy can be.

Patient characteristics, cognitive function, and sensory thresholds can also be included in predictive models.

*Safety Analysis:* The proportion of subjects experiencing adverse events, the nature of the adverse events, as well as severity and relationship of the adverse events to the study will be reported using descriptive statistics. The proportion of subjects with adverse events that led to withdrawal from the study will also be reported. All subjects who received at least one dose of erenumab will be included in the safety analysis.

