#### Instructions:

As part of the research in which you are involved, we are going to test how sensitive your skin is to heat. The testing will use a piece of plastic, called a thermode. We will place the thermode at 4 different locations – each forearm and at 2 locations on the forehead. The thermode will start at about skin temperature, and then get warmer or hot. There are safety limits on the temperature so that you are not injured or burned. Please concentrate on the intensity of the heat that you feel with each test. We will give you a computer mouse which you will use to stop the heating process. With each test, the thermode will get warm and then hot. We want you to press the mouse button the moment that you begin to feel pain. The thermode will then cool off. We will do this three times at each body location. Remember, press the button the moment you begin to feel pain.

LIMITS				
Location	Limit 1	Limit 2	Limit 3	Average
Left Forehead				
Right Forehead				

Right Forearm				
Left Forearm				

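### The Adverse Event form is required for non-serious events only after dosing, with drug causality alone specified, so minor heat or scan injuries at the pre-dose baseline session need not be tabulated

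*Combined protocol and SAP*

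**What the plan says.** Five parts of the combined protocol and SAP bear on this.

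- **Adverse Events (definition).** The definition is not tied to the drug: "The event does not necessarily have a causal relationship with study treatment". The recording duty that comes with it is just as broad and has no start time. It is worded as "ensuring that any adverse events observed by the investigator or reported by the subject are recorded in the", the place being the patient's record.
- **Reporting procedures, non-serious events.** The Adverse Event form is required for events that "occur after the dose of investigational product through the end of the safety follow-up visit (8 weeks after the last dose". The attributes to be assigned include relatedness to the investigational product, judged by a yes/no answer to: "Is there a reasonable possibility that the event may have been caused by the investigational product". No attribute for study procedures is listed.
- **Reporting procedures, serious events.** These are collected if they "occur after signing of the informed consent through the end of the safety follow-up visit". The paragraph just before, on completing the form, also makes the Principal Investigator responsible for "determining the relationship of the adverse event to the study".
- **Analysis Plans, Safety Analysis.** Relationship of events to the study is to be reported descriptively, along with the proportion of participants whose adverse events led to withdrawal. The analysis set is defined thus: "All subjects who received at least one dose of erenumab will be included in the safety analysis".
- **Case Report Forms, questionnaire schedule.** The Adverse Events row carries five marks against six visit columns. Its alignment is lost in the text, but the most natural reading is the first treatment visit through week 12.

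**The concern.** The main non-drug exposure in this study is heat set to a painful level, followed by a scan with further heat stimuli. The QST form tells participants "There are safety limits on the temperature so that you are not injured or burned", so the plan recognises injury as something to be guarded against. Participants first meet this exposure at baseline, where the painful temperature is also first titrated. That is the one session before the drug is given, and so before the form becomes mandatory for non-serious events.

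Two outputs are at stake. The first is the count of minor procedure-related events: a note in a patient's record does not carry the intensity, outcome and causality attributes that the form requires. The second is the relationship result promised in the Safety Analysis. The attribute list and the yes/no question ask only about the product. Staff who follow them literally would answer no for a week-2 skin burn, and nothing else in that list would tie the burn to the thermode.

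**Working it through.** No sample size, power or event rate enters here. The check is a comparison of sections plus session counts.

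**1. Does the baseline session precede the dose?** The Summary says testing and imaging are performed before and after treatment. Table 1 places QST, MRI and the first erenumab treatment all at the baseline visit. The Analysis Plans rely on pre-treatment scans and pre-treatment pain thresholds. The baseline QST and MRI must therefore come before the injection, although the Baseline Visit section does not spell out the order within the visit.

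**2. Is the window's end consistent?** The last dose is at about day 28, and 28 + 56 = 84 days, which is the week-12 visit. The end point agrees with the schedule, so only the start is in question.

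**3. How many sessions lie before the window opens?** QST and MRI are done at baseline, week 2 and week 8, which is 3 sessions.
- Before the first dose: 1 of 3 = 33%.
- Across 50 participants with full attendance (an assumption): 50 × 3 = 150 sessions, of which 50 × 1 = 50 are pre-dose.
- The non-serious rule refers to the dose without saying which one. I take it as the first. Reading it as the second would put week 2 outside as well (2 of 3), but nothing in the documents favours that.

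**4. What exposure does one session contain?**
- Threshold ramps: 4 sites × 3 = 12, each ended by the participant at the onset of pain.
- Ramp-and-hold stimuli: at least 1 painful + 1 non-painful = 2.
- Scanner trials: 3 runs × 9 = 27, a mix of painful, non-painful and no-stimulus trials.

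The holds and scanner trials are all on the left forearm. These figures count exposure, not harm.

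**5. Where does a non-serious baseline skin injury go?**
- Patient's record: yes, under the Adverse Events section.
- Adverse Event form: not required under the non-serious reporting rule. The questionnaire schedule appears to place the form at this visit, without saying whether before or after dosing.
- Safety tables: not assured, because the mandated form data start after the dose.
- If the participant then stops undosed: outside the safety analysis set, and so also missing from the proportion with events leading to withdrawal.

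**6. Where does the relationship result come from?** The non-serious rule specifies product relatedness only. The form-completion paragraph and the Safety Analysis call for relationship to the study. No section defines that broader relationship or names a QST or MRI item to supply it.

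**The case against.** The strongest reply is that the protocol already covers the harms that matter. Any adverse event goes in the patient's record from the outset. Serious events are collected from consent, and the investigator may class a clinically important event as serious, so a bad baseline burn would be captured. Collecting serious events from consent and non-serious ones from dosing is an explicit two-tier choice. The Principal Investigator must judge relationship to the study, which is wide enough to include procedures. The columns of the Adverse Event Flowsheet cannot be read in the available text, so a study-relatedness column may already exist. Painful stimuli are titrated downward when rated too high, and MRI contraindications are excluded. The safety analysis is descriptive.

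Most of this stands, and it rules out two stronger readings that a reader might infer. One is that baseline injuries escape safety collection altogether. They do not: the gap is in form-based reporting and hence in tabulation. The other is that later injuries cannot be attributed to procedures. The duty to judge relationship to the study allows that attribution; what is missing is a specified item to carry it. The lack of heat or MRI hazards under Possible Risks is a separate disclosure matter, and consent pages are not in the available text, so I place no weight on it.

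The reply does not remove the mismatch. The two-tier start does not fit the general definition or, apparently, the form schedule. A record entry does not feed a tabulated result.

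**Conclusion.** The point holds as an inconsistency with a modest practical consequence. As written, the non-serious rule leaves minor heat or scan injuries at 1 of 3 sessions (50 of 150 with full attendance) off the mandatory form, and participants who stop before dosing are outside the safety analysis. The promised relationship to the study has no specified source for procedure-related harm.

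This rests on three assumptions: the dose in the rule is the first dose, baseline QST and MRI precede it, and the form has no procedure item that the text fails to show. The documents give no injury rate and no number expected to stop before dosing, so the number of lost events cannot be estimated. Severity is minor: no aim, primary analysis or sample-size figure depends on it.

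**What to change.** Reconcile the sections with three changes.

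1. In the reporting procedures for non-serious events, start Adverse Event form collection at the first study procedure of the baseline visit, and align the questionnaire schedule with that.
2. List relatedness to a study procedure (QST, MRI or other) as a required attribute beside relatedness to the product. Add a field only if the form lacks one.
3. In the Safety Analysis, report procedure-related events for all participants who began the baseline procedures, and keep drug-related events in dosed participants.

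The cost is wording in two sections, a check of the schedule and at most one form field. The downside is a few more minor events to log, such as transient redness. No dose, stimulus or clinical rule changes.
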